2.8 Safety evaluation

The assessment of safety is based on the type and frequency of Adverse Events (AEs) as well as on the number of laboratory values that fall outside of pre-determined ranges (Common Toxicity Criteria for Adverse Events (CTCAE) grading limits or normal ranges as appropriate). Other safety data include electrocardiogram and vital signs.

The Safety set is used for summaries and listings of safety data with the exception of dose limiting toxicities (DLT) for which the DDS is used.

Differences between treatment received and intended treatment, if any, are provided in a listing.

The overall observation period is divided into three mutually exclusive segments:

1. Pre-treatment period: from day of patient's informed consent to the day before first dose of study medication,
2. On-treatment period: from day of first dose of study medication to 30 days after last dose of study medication,

3. Post-treatment period: starting at Day 31 after last dose of study medication.

Safety summaries are primarily based on all data from the on-treatment period. Following last administration of study medication, adverse events (including serious adverse events), and new antineoplastic therapies are collected for a period of 150 days. Following start of new antineoplastic therapy, only study treatment related adverse events are collected. Select summaries of related adverse events are produced for the overall period starting from the first dose of study treatment until the end of the post-treatment period.

All safety assessments are listed and those collected during the post-treatment period are flagged.

For patients who switch from single-agent LAG525 to combination with PDR001, the on-treatment period is defined from day of first dose of study medication to 30 days after the last dose of single-agent LAG525.

All safety assessments from these patients are listed and the assessments performed under combination and those collected 30 days later than the last dose of single-agent are flagged separately.

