Patients will start LAG525 in combination with PDR001 on Day 1 of the cycle during which the switch is made and patients will resume their standard scheduled visits per [Table 7-1](#). For patients who switch from single-agent LAG525 to LAG525 in combination with PDR001, patients will resume the standard visit schedule; hematology/chemistry labs and vital signs will be collected on Days 8 and 15 as unscheduled assessments for the first cycle upon switch to the LAG525 in combination with PDR001. Cycle 1 will start based on the patient's first dose of the original LAG525 monotherapy. After switching to combination therapy, patients will continue to have efficacy assessments as per protocol; however, the response data from these patients will not be incorporated into the ORR. No additional biopsies will be required. For patients who switch from single-agent LAG525 to LAG525 in combination with PDR001, immunogenicity samples will be collected as unscheduled assessments (instead of their standard PK collection schedule) on Day 1 pre-dose for the first 6 cycles upon switch to the LAG525 in combination with PDR001, and PK blood samples will be collected on Days 1 (pre-infusion) and 8 as unscheduled assessments (instead of their standard PK collection schedule) for the first cycle upon switch to the LAG525 in combination with PDR001. Patients who switch from single agent LAG525 to LAG525 in combination with PDR001 will need to complete an additional End of Treatment Phase Disposition CRF, but the EOT tests/procedures are not required until discontinuation of LAG525 in combination with PDR001.

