### **10.5.3 Safety Objectives**

#### **10.5.3.1 Analysis set and grouping for the analyses**

For summaries of DLTs, the DDS will be used. For all other safety analyses, the safety set will be used. All listings and tables will be presented by treatment group.

The overall observation period will be divided into three mutually exclusive segments:

1. pre-treatment period: from day of patient's informed consent to the day before first dose of study medication
2. on-treatment period: from day of first dose of study medication to 30 days after last dose of study medication
3. post-treatment period: starting at day 31 after last dose of study medication.

Safety summaries will primarily be based on all data from the on-treatment period. Following last administration of study medication, adverse events (including serious adverse events), and new antineoplastic therapies are collected for a period of 150 days. Following start of new antineoplastic therapy, only study treatment related adverse events will be collected. Select summaries of related adverse events will be produced for the overall period starting from the first dose of study treatment until the end of the post-treatment period.

For patients who switch from single-agent LAG525 to combination with PDR001, the on-treatment period will be defined from day of first dose of study medication to 30 days after the last dose of single-agent LAG525.

All safety assessments from these patients will be listed and the assessments performed under combination will be flagged.

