2.2 Analysis sets

The number (%) of patients in each of the defined analysis set will be summarized using the Full Analysis Set (FAS).

Full Analysis Set

The FAS comprises all patients who received at least one full or partial dose of assigned single-agent LAG525, or at least one full or partial dose of assigned combination of study drugs. Patients will be analyzed according to the planned treatment. The FAS will be used for all listings of raw data. Unless otherwise specified, the FAS will be the default analysis set used for all analyses.

Safety Set

The Safety Set includes all patients from the FAS who have received at least one dose of LAG525 or PDR001. Patients will be classified according to treatment received, where treatment received is defined as:

1. The treatment assigned if it was received at least once, or
2. The first treatment received when starting therapy with study treatment if the assigned treatment was never received.

The safety set will be used for the safety summary of the study.

Per-Protocol Set

The Per Protocol Set (PPS) consists of a subset of FAS patients in the phase II part who meet the following criteria:

- Presence of at least one measurable lesion according to RECIST 1.1 as per Study Protocol Appendix 1
- At least 2 post-baseline tumor assessments (unless disease progression according to RECIST 1.1 is observed before that time)
- Have received the planned treatment

Patients will be classified according to planned treatment.

The PPS will be used in the phase II part of the study only and will define the patients used in the sensitivity analysis of the primary endpoint. If the PPS and the FAS are identical, then analyses described by the PPS below will not be performed.

Dose- Determining Analysis Set

Single agent LAG525 escalation cohort

The dose-determining analysis set (DDS) consists of all patients from the safety set in the dose escalation part who either meet the minimum exposure criterion and have sufficient safety evaluations, or have experienced a DLT during Cycle 1.

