2.8.1.2 Data analysis

Primary summary tables for AEs will include only AEs that started or worsened during the on-treatment period.

The incidence of treatment-emergent AEs (new or worsening from baseline) will be summarized by system organ class and /or preferred tem, severity (based on CTCAE grades),

type of AE and relation to study treatment by treatment group. Serious adverse events and non-serious adverse events will be tabulated.

All deaths (on-treatment and post-treatment) will be summarized. All deaths are considered to be due to study indication.

All AEs collected in the AE (e)CRF page will be listed along with the information collected on those AEs e.g. AE relationship to study treatment, AE outcome etc. AEs starting during the pre or post-treatment periods will be flagged in the listings.

AEs will be summarized by number and percentage of patients having at least one AE in each primary system organ class (SOC) and for each preferred term (PT) using MedDRA coding. Occurrences of an AE will be counted only once in the respective AE category. A patient with multiple CTCAE grades for the same preferred term will be summarized under the maximum CTCAE grade recorded for the event. AE with missing CTCAE grade will be included in the 'All grades' column of the summary tables.

In AE summaries the primary system organ class will be presented alphabetically and the preferred terms will be sorted within primary SOC in descending frequency. The sort order for the preferred term will be based on their frequency in all patients.

The following adverse event summaries will be produced by treatment for AEs starting or worsening during the on-treatment period:

- Overview of adverse events and deaths (number and % of patients who died, with any AE, any SAE, any AE leading to dose reductions/interruptions, AE leading to discontinuation)
- AEs by SOC and PT, summarized by relationship (all AEs and AEs related to study treatment);
- Seriousness (SAEs, and non-SAEs);
- Leading to treatment discontinuation;
- Leading to dose interruption/adjustment;
- Requiring additional therapy;
- Dose limiting toxicities by PT

The following listings will be produced:

- All adverse events (safety set)

Deaths (CSR Outputs)

On-treatment deaths are summarized produced by preferred term.

All deaths will be listed for the safety set, deaths occurring after the on-treatment period will be flagged.

EudraCT and clinicaltrials.gov requirements for AEs and Deaths summaries

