2.8.2.3 Data analysis

Laboratory data from all sources (central and local laboratories (as applicable)) will be combined. The summaries will include all assessments available for the lab parameter collected no later than 30 days after the last study treatment administration date (see [Section 2.8](#)).

The following listing will be produced for the laboratory data:

- Listing of all CTC grade 3 or 4 laboratory toxicities

The following by-treatment summaries will be generated separately for hematology and biochemistry tests:

- Worst post-baseline hematology and biochemistry based on CTC grades

For laboratory tests where grades are defined by CTCAE 4.03:

- Shift tables using CTCAE 4.03 grades to compare baseline to the worst on-treatment value

For laboratory tests where grades are not defined by CTCAE 4.03:

- Shift tables using the low/normal/high/ (low and high)

[Table 2-3](#) and [Table 2-4](#) list all laboratory parameters for which CTCAE grades are defined and for which CTCAE grades will be listed on local laboratory normal ranges respectively.

Table 2-3 Laboratory parameters for which CTCAE grades are defined

Hematology and coagulation		Biochemistry	
White Blood Cells (WBC)	↑↓	Creatinine	↑
Hemoglobin	↓	Sodium	↑↓
Platelets counts	↓	Potassium	↑↓
Absolute Neutrophils	↓	Corrected calcium	↑↓
Absolute Lymphocytes	↑↓	Magnesium	↑↓
		Albumin	↓
		AST (SGOT)	↑
		ALT (SGPT)	↑
		Total Bilirubin	↑
		Inorganic Phosphorus	↓
		amylase	↑
		lipase	↑
		Alkaline phosphatase	↑
		Fasting Glucose	↑↓

↑ Indicates that CTC grade increases as the parameter increases.

↓ Indicates that CTC grade increases as the parameter decreases.

Table 2-4 Laboratory parameters (without CTCAE grades) for which lab reference ranges are defined

Hematology and coagulation	Biochemistry
Hematocrit	Blood urea nitrogen (BUN)
Absolute Basophils	Urea*
Absolute Eosinophils	
	Direct Bilirubin
Absolute Monocytes	Indirect Bilirubin
	T4
	T4FR
	TSH
	Chloride
	Bicarbonate

*Urea will be converted to BUN and reported as BUN.

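### The on-treatment window for patients who switch from single-agent LAG525 to LAG525+PDR001 is not cut at the switch, so early combination adverse events are counted as single-agent events

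*SAP*

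**What the plan says.** SAP 2.8 gives switchers their own rule: "the on-treatment period is defined from day of first dose of study medication to 30 days after the last dose of single-agent LAG525". Protocol 10.5.3.1 agrees: "the on-treatment period will be defined from day of first dose of study medication to 30 days after the last dose of single-agent LAG525". Neither text mentions the first combination dose as an end point.

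Four other provisions decide where the events go:

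- **Start of the combination (Protocol 6.2.3.2.1).** "Patients will start LAG525 in combination with PDR001 on Day 1 of the cycle during which the switch is made".
- **Treatment group (SAP 2.2, Safety Set).** Treatment received is "The treatment assigned if it was received at least once", so a switcher remains under single-agent LAG525.
- **AE tables (SAP 2.8.1.2).** "Primary summary tables for AEs will include only AEs that started or worsened during the on-treatment period", and incidence is reported by treatment group.
- **Handling of combination data (SAP 2.8).** The safety assessments of switchers are listed, and "the assessments performed under combination and those collected 30 days later than the last dose of single-agent are flagged separately". This concerns listings. No provision removes these events from the tables.

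**The concern.** Single-agent safety and tolerability is a secondary objective, and its AE tables should describe patients who are on the single agent. Under the current rule they also contain events that began after PDR001 was added. The rule can only add such events to the single-agent columns.

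Eligibility for the switch makes this more visible. Protocol 6.2.3.2.1 requires at least four monotherapy cycles without a treatment-related toxicity of grade 2 or higher. If that is followed, any related event of that grade in the overlap is one the patient did not have before the switch.

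The plan separates the two treatments elsewhere. Efficacy is censored at the start of PDR001 (Protocol 10.5.2) or at the last adequate assessment before the switch (SAP 2.7.2). Dose-limiting toxicities after the switch are left out of the dose-escalation model (Protocol 10.1.4). Only the general safety tables run across the switch.

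**Working it through.** The plan gives no figure for the overlap, so there is nothing to reproduce. The check is date arithmetic.

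**Inputs**

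- Day 0 is the last single-agent dose. The window runs to day 30 inclusive (SAP 2.8, Protocol 10.5.3.1).
- The first combination dose falls on day s. On schedule, s is one dosing interval: 14 for Q2W and 28 for Q4W. These are the two schedules that SAP 2.5.1.1 lists for Arms A and C.
- Delays are assumptions, because the documents do not give the actual gaps.

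**Overlap = max(0, 30 − s + 1)**, counting the switch day.

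| Schedule | Start of combination | s | Overlap (days) |
|---|---|---|---|
| Q2W | on schedule | 14 | 30 − 14 + 1 = 17 |
| Q2W | 7 days late | 21 | 30 − 21 + 1 = 10 |
| Q2W | 14 days late | 28 | 30 − 28 + 1 = 3 |
| Q2W | 21 days late | 35 | 0 |
| Q4W | on schedule | 28 | 30 − 28 + 1 = 3 |
| Q4W | 3 days late | 31 | 0 |

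The overlap is zero for any s above 30.

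**Laboratory values.** Samples on dosing days are taken before the infusion (Protocol 7.2.2.5), so the switch-day sample is still single-agent data. After the switch, "hematology/chemistry labs and vital signs will be collected on Days 8 and 15 as unscheduled assessments for the first cycle upon switch". These draws fall on days s + 7 and s + 14. For an on-schedule Q2W switch they are days 21 and 28, both inside the window. For Q4W they are days 35 and 42, both outside.

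**Weight of one patient.** The Amendment 10 study status gives 134 single-agent patients. A switcher who has a preferred term in the overlap that did not occur on monotherapy adds 1/134 = 0.7 percentage points to a fully pooled column. SAP 2.1 presents Phase I safety by dosing regimen. At least eight single-agent regimens are documented: seven in Protocol Table 14-22, and at least one at 15 mg/kg (Protocol 1.2.3.2). As an illustration only, an average column then has at most 134/8 = 16.75 patients, and one such switcher adds 1/16.75 = 6.0 points. Actual column sizes are not given.

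**With a cut at the first combination dose,** the overlap is zero on every schedule. Follow-up after the last single-agent dose becomes about 14 of 30 days (Q2W) or 28 of 30 days (Q4W).

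**The case against.** The strongest reply is that the rule is deliberate. Protocol and SAP agree on it, and it applies the study's ordinary 30-day tail to the single-agent period. LAG525 continues after the switch, normally at the same dose. Its median half-life ranges from 7.4 to 15.4 days (Protocol 1.2.3.2), and the protocol notes that some immune-related events appear late, although it says this of immune combinations (Protocol 6.2.4). An event soon after PDR001 is added may therefore come from earlier LAG525 exposure, and keeping it in the single-agent table is cautious in a first-in-human study. Efficacy has no comparable carry-over tail, so censoring it at the switch does not prove an inconsistency. The table shells and dataset specifications are not public and might already contain a footnote or a split.

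The carry-over argument stands as a cost of the change. It does not justify the present rule, because the table cannot show which events are carry-over and which arose with PDR001. A separate switcher summary keeps both visible.

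Some stronger inferences are not supported:

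- *The laboratory tables take in even more combination data.* SAP 2.8.2.3 uses values "collected no later than 30 days after the last study treatment administration date", and the general definition in SAP 2.1.1 includes the combination partner. A reader might conclude that the window for switchers follows the last combination dose. But 2.8.2.3 refers to Section 2.8, where the specific switcher rule stands, so that rule most naturally governs. A cross-reference is enough.
- *The overlap could exceed 17 days through an early switch.* The seven-day window in Protocol 7.1 covers visits, tests and procedures. The dosing text speaks only of delays.
- *The Amendment 08 rationale gives the number of switchers.* It speaks of patients without other access to a PD-1 inhibitor and is not a count.
- *Exposure in SAP 2.5.1.1 must change too.* No effect on a reported result has been shown.

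**Conclusion.** The point holds for the AE tables. As written, AEs that start or worsen between the first combination dose and day 30 after the last single-agent dose are counted under single-agent LAG525. The overlap is 17 days (Q2W) or 3 days (Q4W) for an on-schedule switch and disappears when the gap exceeds 30 days.

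The total effect cannot be computed, because neither the number of switchers nor the actual gaps are given. It is probably small, and for Q4W close to nil. The tables are descriptive and no decision rule depends on them. A reader might infer that dose selection or the response rate is affected. The documents rule that out: post-switch dose-limiting toxicities are excluded from the model (Protocol 10.1.4) and post-switch responses from the response rate (Protocol 6.2.3.2.1). The conclusion assumes that the unseen table shells do not already separate these events.

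**What to change.** By SAP amendment or addendum, recorded as a change from Protocol 10.5.3.1 so that the two documents do not silently diverge:

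1. End the switchers' single-agent on-treatment period at the earlier of the last single-agent dose + 30 days and the first combination dose.
2. Keep switch-day assessments that the protocol schedules before dosing as single-agent data. SAP 4.1 already uses this convention for baseline.
3. Work at date level for AEs, since Protocol 8.1.1 asks for start and end dates only. AEs with a start or worsening date on or after the first combination dose date go to a separate switcher summary. This would also cover combination AEs after day 30, which are now outside the primary AE tables.
4. State a rule for partial AE dates relative to the switch date. SAP Table 4-1 imputes only against study treatment start. An AE with a missing day in the switch month would be set to the first of that month, which is on or before the switch.
5. Add a cross-reference to this rule in SAP 2.1.1 and 2.8.2.3.

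The cost is the wording, a derived switch date and one small table. Single-agent follow-up after the last dose shortens (Q2W from 30 to about 14 days), and some early post-switch events that may be due to LAG525 alone move to the switcher table.

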2.8.1 Adverse events (AEs)

2.8.1.1 Data handling

Adverse events will be coded using the Medical dictionary for regulatory activities (MedDRA) and assessed according to the Common Terminology Criteria for Adverse Events (CTCAE) version 4.03, respectively.

The CTCAE represents a comprehensive grading system for reporting the acute and late effects of cancer treatments. CTCAE grading is by definition a 5-point scale generally corresponding to mild, moderate, severe, life threatening, and death. This grading system inherently places a value on the importance of an event, although there is not necessarily proportionality among grades (a grade 2 is not necessarily twice as bad as a grade 1).

If CTCAE grading does not exist for an AE, grades 1, 2, 3, or 4 corresponding to the severity of mild, moderate, severe, and life-threatening, respectively, will be used. CTCAE grade 5 (death) is not used in this study. Death information will be collected on the “Death” eCRF pages.

2.8.1.2 Data analysis

Primary summary tables for AEs will include only AEs that started or worsened during the on-treatment period.

The incidence of treatment-emergent AEs (new or worsening from baseline) will be summarized by system organ class and /or preferred tem, severity (based on CTCAE grades),

type of AE and relation to study treatment by treatment group. Serious adverse events and non-serious adverse events will be tabulated.

All deaths (on-treatment and post-treatment) will be summarized. All deaths are considered to be due to study indication.

All AEs collected in the AE (e)CRF page will be listed along with the information collected on those AEs e.g. AE relationship to study treatment, AE outcome etc. AEs starting during the pre or post-treatment periods will be flagged in the listings.

AEs will be summarized by number and percentage of patients having at least one AE in each primary system organ class (SOC) and for each preferred term (PT) using MedDRA coding. Occurrences of an AE will be counted only once in the respective AE category. A patient with multiple CTCAE grades for the same preferred term will be summarized under the maximum CTCAE grade recorded for the event. AE with missing CTCAE grade will be included in the 'All grades' column of the summary tables.

In AE summaries the primary system organ class will be presented alphabetically and the preferred terms will be sorted within primary SOC in descending frequency. The sort order for the preferred term will be based on their frequency in all patients.

The following adverse event summaries will be produced by treatment for AEs starting or worsening during the on-treatment period:

- Overview of adverse events and deaths (number and % of patients who died, with any AE, any SAE, any AE leading to dose reductions/interruptions, AE leading to discontinuation)
- AEs by SOC and PT, summarized by relationship (all AEs and AEs related to study treatment);
- Seriousness (SAEs, and non-SAEs);
- Leading to treatment discontinuation;
- Leading to dose interruption/adjustment;
- Requiring additional therapy;
- Dose limiting toxicities by PT

The following listings will be produced:

- All adverse events (safety set)

Deaths (CSR Outputs)

On-treatment deaths are summarized produced by preferred term.

All deaths will be listed for the safety set, deaths occurring after the on-treatment period will be flagged.

EudraCT and clinicaltrials.gov requirements for AEs and Deaths summaries

For the legal requirements of clinicaltrials.gov and EudraCT, two required tables on treatment-emergent adverse events which are not serious adverse events with an incidence greater than 5% and on treatment emergent SAEs and SAEs suspected to be related to study treatment will be provided by SOC and PT on the safety set population.

If for a same patient, several consecutive AEs (irrespective of study treatment causality, seriousness and severity) occurred with the same SOC and PT:

- a single occurrence will be counted if there is ≤ 1 day gap between the end date of the preceding AE and the start date of the consecutive AE
- more than one occurrence will be counted if there is > 1 day gap between the end date of the preceding AE and the start date of the consecutive AE

For occurrence, the presence of at least one SAE / SAE suspected to be related to study treatment / non SAE has to be checked in a block e.g., among AE's in a ≤ 1 day gap block, if at least one SAE is occurring, then one occurrence is calculated for that SAE.

The number of deaths resulting from SAEs suspected to be related to study treatment and SAEs irrespective of study treatment relationship, will be provided by SOC and PT.

